10.8 SAFETY MONITORING AND REPORTING

PROPRIETARY AND CONFIDENTIAL

Oui Therapeutics, Inc. | [name]

Suicidal ideation/behaviors and other clinical outcomes will be assessed at the Week 0 and Week 12 follow-up assessments. Week 0 is the study baseline assessment, which occurs while the participant is housed in an inpatient treatment facility. For purposes of risk management, results of the study assessment at Week 0 will be shared with the inpatient treatment team in order to provide information relevant to their treatment/discharge planning. The 12 week follow up assessment is conducted by phone. In order to facilitate risk management during study interview calls, we will do the following:

- 1) Only enroll participants who are able to provide at least one verifiable contact for emergency or tracking purposes;
- 2) Obtain location information at the start of each phone assessment; and
- 3) Schedule assessments at a time when the parent/guardian is present at the same location as the participant.

Each youth assessment session will begin by confirming via telephone/video whether the youth and guardian are together. Increases in suicide risk will be communicated to the parent/guardian and outpatient provider (see Appendix B). In addition, interviewers will engage in risk management interventions as clinically indicated following the guidelines outlined in the Risk Management Plan (see Appendix B). Participants will be informed that information they input to the digital platform is not monitored for purposes of risk assessment.

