1.2 STUDY SCHEMA

Screening

Week 0

Total N: 20
Screen potential participants by inclusion and exclusion criteria. Conduct informed consent/assent process
Baseline assessments: Demographics, Support Adult Information Form, Psychiatric history, Medication use, SIQ-JR, PHQ-2, FSPC, SPS, Sources of Strength Coping Scale, C-SSRS, CSI, CHCQ
Enroll in eYST

Weeks 1-12

Implement eYST
Week 4/8 assessments: SUS, User feedback questions, FIM, AIM, IAM, CSQ-I, CSI, SUS

Post-intervention Assessments: Medication use, SIQ-JR, PHQ-2, FSPC, SPS, Sources of Strength Coping Scale, User feedback questions
Adolescents' use of adult support, C-SSRS

Weeks 12-14

PROPRIETARY AND CONFIDENTIAL

Oui Therapeutics, Inc. | [name]

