1.3 SCHEDULE OF ACTIVITIES

Table 1. Schedule of Assessments

		Study Periods											
		Intervention											
Week (W)	W0	W1	W2	W3	W4	W5	W6	W7	W8	W9	W10	W11	W12*
Informed Consent / Assent	Y, P, A												
Demographics, Contact, and Information Form	Y, P, A												
Medical Chart Abstraction (Completed by study staff)	Y												
Medication use	Y*												Y*
Chronic Health Conditions Questionnaire (CHCQ)	Y*												
Enrollment in eYST	Y, P, A												
Suicide Ideation Questionnaire Jr (SIQ-JR)	Y												Y
Patient Health Questionnaire-2 (PHQ-2)	Y												Y

PROPRIETARY AND CONFIDENTIAL

Oui Therapeutics, Inc. | [name]

		Study Periods											
		Intervention											
Week (W)	W0	W1	W2	W3	W4	W5	W6	W7	W8	W9	W10	W11	W12*
Family, School, and Peer Connectedness (FSPC)	Y												Y
Social Provisions scale (SPS)	Y												Y
Sources of Strength Coping Scale	Y												Y
System Usability Scale (SUS)					Y, P					A			
User feedback questions					Y, P					A			A
Feasibility of Intervention Measure (FIM)					Y, P					A			
Acceptability of Intervention Measure (AIM)					Y, P					A			
Intervention Appropriateness Measure (IAM)					Y, P					A			
Client Satisfaction Questionnaire (CSQ-I)					Y, P					A			
Cornell Services Index (CSI)	Y*												Y*

PROPRIETARY AND CONFIDENTIAL

Oui Therapeutics, Inc. | [name]

		Study Periods											
		Intervention											
Week (W)	W0	W1	W2	W3	W4	W5	W6	W7	W8	W9	W10	W11	W12*
Columbia-Suicide Severity Rating Scale (C-SSRS)	Y												Y
Adolescents' use of 'caring adult' support (quality, amount)													Y
Measures Administered via eYST													
Presenting Concerns	Y*												
eYST Check ins		A	A	A	A	A	A	A	A	A	A	A	A

Y = Youth | P = Parent | A = Support Adult |

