Columbia-Suicide Severity Rating Scale (C-SSRS)	Adverse Events related to Suicidal Ideation and/or Behaviors	Adverse event monitoring will be assessed with the Columbia-Suicide Severity Rating Scale (C-SSRS). The C-SSRS is a semi-structured, rater-based interview to assess the severity and intensity of SI and behaviors (Mundt et al., 2013).
	Demographics, Contact, and Information Form	Interviewer will ask participants their age, gender identity, sex, race/ethnicity
	Medical Abstraction Form	Current psychiatric diagnoses will be obtained by reviewing admission reports and electronic medical records.
	Medication use	Youth medication use will be recorded using a combination of medical record review and parent/youth interview. The following information will be recorded for each medication: name, indication, dose, frequency, start, and end date.
Cornell Services Index (CSI)	Treatment Utilization	Treatment utilization will be assessed using the CSI, an interview-based method that assesses engagement in health treatment (e.g., outpatient psychotherapy, inpatient hospitalization).
Chronic Health Conditions Questionnaire (CHCQ)	Chronic Health Conditions	A 31-item questionnaire adapted from the National Survey of Children's Health (2022) to obtain current and past chronic health conditions and their severity among youth participants.
Adolescents' use of 'caring adult' support	Quality/Frequency of support	The Adolescents' use of 'caring adult' support will ask youth about their interactions with their support adults to better understand how they are using eYST for social support.
eYST platform measures	Youth concerns and support progress	Parents will provide information about current concerns for youth. Support persons will complete 12 weekly check-ins via the eYST platform to indicate progress with youth.

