10.2 ADVERSE EVENTS

Adverse Events (AEs) will be monitored and documented at each study visit. Reporting of AEs will follow Michigan Medicine Institutional Review Board Policy and NIMH policy. Given that all enrolled participants will have a history of suicidal ideation with plan, AEs related to suicidal thoughts/behaviors will be categorized as “expected”.

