10.7 REPORTING PERIOD

In this study, all adverse events are collected starting at the time informed consent has been signed. AEs are collected until the last study visit and exit from the study.

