Careful monitoring of risk status over time and solid clinical decision-making require up-to-date documentation of each adolescent's risk status. These will be kept in secured files where they will be available to the Principal Investigator and research staff. In addition to follow-up if participant meets high risk criteria, a risk status review will be conducted by the study Principal Investigator and/or Co-Investigator ([name] & [name]) on a regular basis to ensure that each participant's risk status was correctly identified and recorded. These review documents will be kept securely.

DETERMINATION OF RISK STATUS AND DEFINITION OF HIGH RISK

If the adolescent expresses suicidal ideation or behaviors consistent with one or more of the high-risk criteria outlined below at the time of the baseline assessment or 3-month follow-up assessment, research staff will notify the attending/treatment team of information learned (if

PROPRIETARY AND CONFIDENTIAL

Oui Therapeutics, Inc. | [name]

during psychiatric inpatient stay) or the senior on-call clinician (if assessment occurs outside of inpatient unit) immediately. Follow-up assessments will be completed by phone by a trained study team member who will contact supervising clinician (PhD level, licensed clinical psychologist) immediately if a youth meets high-risk criteria.

Definition of High Risk

- (1) Suicidal ideation in the past week with thoughts of a method, plan, or intent (C-SSRS items 3-5)
- (2) A suicide attempt since baseline assessment (per C-SSRS) and no psychiatric evaluation was conducted following this attempt (no ED visit or psychiatric hospitalization).
- (3) A verbal statement of clear suicidal intent or a plan to attempt suicide.

MANAGEMENT OF HIGH RISK STATUS

1. Procedures

If a participant meets one or more of the above criteria, the project staff member may ask one or more of the following additional questions to help in determining next steps. Responses are recorded in the Action Plan form.

In the last week...

- *Has the participant experienced suicidal ideation?*
- *Has the participant thought of a plan for how to kill self?*
- *Has there been alcohol or drug use?*
- *Have there been any psychotic signs or symptoms?*

And...

- *Has the participant talked about their past week suicidal ideation or behaviors with a provider or with a guardian?*
- *Does the participant have access to a firearm?*

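### Section 10.2 requires AE monitoring at every visit, but the protocol specifies no suicidality or AE question for the Week 4 youth session

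*Combined protocol and SAP*

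**What the plan says.** Section 10.2 sets the duty: "Adverse Events (AEs) will be monitored and documented at each study visit". Section 10.7 starts collection at signed consent and adds that "AEs are collected until the last study visit and exit from the study".

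The assessment table in Section 8.1 names the tool for suicidality-related events: "Adverse event monitoring will be assessed with the Columbia-Suicide Severity Rating Scale (C-SSRS". No other AE instrument is named.

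Section 10.8 gives the timing: "Suicidal ideation/behaviors and other clinical outcomes will be assessed at the Week 0 and Week 12 follow-up assessments". Table 1 (Section 1.3) agrees. Its C-SSRS row marks youth at W0 and W12 and is blank between, and there is no AE row.

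Youth do have an interim session. Table 1 gives them forms at W4, and Section 8.7 pays for it. Section 8 also mentions Week 8, but refers to Table 1 for content, and Table 1 has no youth measure there. The schema in Section 1.2 reads "Week 4/8 assessments: SUS, User feedback questions, FIM, AIM, IAM, CSQ-I, CSI, SUS", whereas Table 1 has the CSI, reported by the parent, at W0 and W12 only.

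In Appendix B, the sentence on high-risk determination speaks of criteria met "at the time of the baseline assessment or 3-month follow-up assessment".

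**The concern.** Section 10.4 names increased suicidality and suicide-related hospitalization as the primary anticipated events, and Section 10.1 states a safety hypothesis. Both depend on how well these events are found. The protocol requires AE monitoring at Week 4 but does not say there how it is done: the one named tool is not scheduled, and nothing listed takes its place.

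Two things are at stake. The first is timeliness. The weeks after an inpatient stay for suicide risk include a paid youth contact at which no listed instrument asks about that risk. The second is the completeness of the safety count. With a single post-baseline structured assessment at Week 12, a youth who attends Week 4 and is then lost has no structured suicidality data after baseline. Section 12.1.1 will report completion of assessment appointments, but nothing ties that figure to the suicidality AE count. A low count could then reflect few events or few youth ascertained.

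**Working it through.** The plan has no figure of its own to reproduce. The check compares sections and then does schedule arithmetic.

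1. **Duty against means.** Every visit (10.2), from consent to exit (10.7), with the C-SSRS as tool (8.1). Tool scheduled at W0 and W12 (10.8, Table 1). Text and table agree, so this is not a table-reading problem. W4 is a visit without the tool.

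2. **What youth complete at W4.** Table 1 lists SUS, user feedback, FIM, AIM, IAM and CSQ-I: 6 forms, of which 0 concern suicidality or AEs. Adding the CSI, as the schema does, makes 6 + 1 = 7. The CSI records service use, including inpatient stays, so 1 of 7 could pick up a readmission, but still 0 of 7 ask about ideation or behavior. The gap holds on either reading.

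3. **Longest interval between structured checks.** Now: 12 − 0 = 12 weeks. With W4 added: max(4 − 0, 12 − 4) = max(4, 8) = 8 weeks.

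4. **Structured post-baseline checks per youth.** Now 1 (W12). With W4 added: 2 (W4, W12).

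5. **A youth seen at W4 and lost before W12.** Structured post-baseline coverage now: 0 of 12 weeks. With a since-last-contact query at W4: 4 of 12 weeks.

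6. **How many such youth.** The documents give no dropout rate. Section 12.1.3 cites 15 as enough for serious usability issues and recruits 20 to allow for dropout. As an assumption, that allows for 20 − 15 = 5 losses, or 5/20 = 25%. The number lost between W4 and W12 would then lie anywhere from 0 to 5. Youth lost before W4 are not helped by a W4 query.

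7. **Burden.** 20 youth × 1 query = at most 20 administrations.

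**The case against.** The strongest reply is that safeguards exist and apply at Week 4. Much of it stands.

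- A reader might infer that AEs go uncollected at Week 4. The documents do not support that: Section 10.2 covers the visit. Section 12.2 promises structured capture of all study outcomes, and Section 13.2 mentions a data safety and monitoring plan and AE training. A visit-level AE form may exist outside this protocol, so it cannot be said that the question is left to the interviewer's choice.
- A reader might infer that Appendix B operates only at baseline and Week 12. One sentence names those times. But its general guidelines follow up any sign of raised risk and send any participant who meets the high-risk criteria to the Action Plan. The sentence on telephone follow-up assessments is also not limited to one visit, and Section 10.8 has interviewers manage risk as clinically indicated. A disclosure at Week 4 would be acted on.
- A reader might infer that the high-risk criteria cannot be met without a C-SSRS. The first criterion, "Suicidal ideation in the past week with thoughts of a method, plan, or intent (C-SSRS items 3-5"), describes a state that a youth could simply report.
- Licensed specialists have weekly calls with support adults, so other routes of detection exist, and no average delay in detection can fairly be computed from the visit schedule alone.
- For youth who reach Week 12, the second high-risk criterion looks back to baseline for attempts, so a long gap does not by itself mean attempts are missed. That look-back is written for attempts; the ideation criterion covers the past week.

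What remains is that these safeguards mostly respond to a sign once it appears. The weekly calls are with support adults, and Section 10.8 says platform entries are not monitored for risk. This protocol specifies no question to the youth at Week 4 that would bring a sign out.

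**Conclusion.** The point holds as a gap in structured elicitation. The protocol imposes AE monitoring at every visit, names one tool for suicidality events, and does not schedule it at the only interim youth session in Table 1. The size is 1 structured post-baseline check instead of 2, a longest gap of 12 weeks instead of 8, and no structured post-baseline suicidality data for youth lost between Weeks 4 and 12, whose number is unknown.

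This rests on the protocol text alone; a safety monitoring plan or case report form held elsewhere may already contain the question, in which case the protocol should say so. It does not show that events would be ignored, or that attempts would be missed among youth who complete Week 12. In a 20-youth feasibility study that disclaims conclusions about effects, this is a cheap improvement that should be made.

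**What to change.** 1. Add a brief since-last-contact C-SSRS/AE query to the existing Week 4 youth session, and add an AE row to Table 1.
2. Amend Section 10.8 so that suicidality is assessed at Weeks 0, 4 and 12, and name Week 4 in the Appendix B high-risk sentence.
3. Reconcile the CSI: either it is asked at Week 4, as in the schema, or it is not, as in Table 1.
4. Report suicidality AEs out of all enrolled youth (20 planned), with the number not ascertained at Week 12. For those youth, use the alternative sources that Section 12.2 already allows, where consent permits.

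The cost is wording in a few sections and a few minutes for each of up to 20 youth. Under Section 8.1 each youth session already opens with a telephone or video check that the guardian is present, and Appendix B already provides trained staff with a supervising clinician to contact. There would be some record or contact checking for youth who miss Week 12. The event count may look less favourable because more is asked. No sample size or power figure changes.

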11. CLINICIAN TRAINING AND SUPERVISION

The original YST manual and measure will be updated to fit the eYST procedures. The eYST platform will provide explicit guidelines (including model scripts) to clinicians regarding intervention components (e.g., facilitating youth nominations, conducting the support adult psychoeducation sessions and check-ins). YST-Is will be licensed mental health professionals with training and experience in adolescent mental health and suicide risk assessment. YST-Is will complete YST-specific training and must successfully complete a certification exam that assesses knowledge of YST components and intervention competencies (via roleplays of psychoeducation session units and telephone check-ins). Additionally, weekly supervision will be provided (individually or in small groups) to YST-Is by a clinical psychologist.

All psychoeducation and weekly check-in sessions will be taped with 25% of sessions reviewed by [name] and/or [name] for clinical supervision and for coding of the successful completion of key components. In addition, YST-Is will complete session checklists following each psychoeducation session as a self-check for coverage of key components.

12. STATISTICAL CONSIDERATIONS

12.1 STATISTICAL PROCEDURES AND DATA ANALYSIS

12.1.1 Primary Effectiveness: Definition of Success (or Failure) of the Endpoint

AIM 1: We will use content analysis to identify themes from qualitative data([Hsieh & Shannon, 2005](#)). Using two raters, transcribed responses will be grouped into themes and a summary of lessons learned. Our team will identify required adaptations for implementing and adopting eYST and use these findings to advise on all subsequent eYST development. We will

PROPRIETARY AND CONFIDENTIAL

Oui Therapeutics, Inc. | [name]

Oui Therapeutics, LLC Aviva (OTX-202)	Digital Youth-Nominated Support Team (YST) Program	Informed Consent Form Clean Copy Page 32
--	---	---

use the Consolidated Criteria for Reporting Qualitative Research Checklist (COREQ) ([Tong et al., 2007](#)) to provide a detailed report of all qualitative research methods used in our project.

AIM 2: For quantitative data, descriptive statistics will be calculated to examine feasibility and acceptability, including rates of recruitment and eligibility, completion of eYST tasks (for each user type) and completion of assessment appointments. The benchmark for success is for eYST to be rated as usable (i.e. average System Usability Scale (SUS) score = 68 or above). Also, eYST's feasibility measures, such as percentage of nominated adults agreeing to participate in the study and percentage of youth having 3 or more adults participating in the psychoeducation session, must be comparable to metrics from prior YST studies.

12.1.2 Rationale

A single arm design (vs. a controlled design) is appropriate as the workflow for eYST has not been implemented elsewhere. At the end of this study, we will know how to support implementation fidelity, which is key for a future RCT.

Missing data: For missing post-tests, we will use a last observation carried forward imputation, as more sophisticated missing data methods are not appropriate for our sample size.

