12.1.3 Justification of sample size-suicide attempts

No power calculation was used to determine sample size because this is an exploratory feasibility study ([Jones et al., 2003](#)). Research shows that 5 participants are sufficient to detect 80% of usability issues ([Bailey, 2005](#); [Nielsen & Faber, 1996](#)) and 15 are sufficient to detect serious usability issues ([Spool & Schroeder, 2001](#)). Therefore, we plan to recruit 20 youth participants, accounting for dropouts.

We will not make conclusive statements about intervention effects due to the small sample size, the single arm design and the fact that clinical improvement may be expected with the passage of time (i.e., without eYST), especially post inpatient admission.

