12.1.5 Secondary Endpoints

Analysis of our exploratory outcomes associated with YST including suicidal thoughts and behaviors, healthcare service utilization, and perception of social support will be conducted only to document the extent and variation of change across subjects. The results of these analyses will be interpreted with great caution given the small sample size and single arm design. Clinically Significant Change (CSC) is a metric that can be applied to assess within patient change at the individual level. We will document the percentage of participants who experience CSC from baseline to 12 weeks on the outcomes of interest using procedures described by Morley and Dowzer ([Morley & Dowzer, 2014](#)). We will compare patterns of change from baseline to follow-up periods to parallel data from a former RCT of YST ([[name] et al., 2009](#)).

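### For the youth clinical measures taken only at weeks 0 and 12, last observation carried forward is baseline carried forward: a youth with no later value is recorded as unchanged (minor)

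*Combined protocol and SAP*

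**What the plan says.** The missing-data rule is one sentence in section 12.1.2: "For missing post-tests, we will use a last observation carried forward imputation". The reason given is that the sample is too small for more elaborate methods. No measure is exempted and no sensitivity analysis is named.

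On timing, section 10.8 states: "Suicidal ideation/behaviors and other clinical outcomes will be assessed at the Week 0 and Week 12 follow-up assessments". Table 1 in section 1.3 agrees. It marks SIQ-JR, PHQ-2, FSPC, SPS, the Sources of Strength scale and C-SSRS at W0 and W12 and at no week between. Sections 4.1 and 8 speak of assessments at weeks 4, 8 and 12, but in Table 1 the intermediate ones are the usability, feasibility, acceptability, appropriateness and satisfaction measures.

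Section 12.1.5 puts the clinical outcomes to three uses. The analysis "will be conducted only to document the extent and variation of change across subjects". Then: "We will document the percentage of participants who experience CSC from baseline to 12 weeks on the outcomes of interest". And: "We will compare patterns of change from baseline to follow-up periods to parallel data from a former RCT of YST".

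On losses, section 12.1.3 says only: "Therefore, we plan to recruit 20 youth participants, accounting for dropouts". Section 12.2 allows the team to try for a final assessment before consent is withdrawn, but does not require one.

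**The concern.** With two scheduled visits, the last observation before a missing second one is the first. The rule therefore supplies no information about follow-up; it asserts that the youth did not change. That matters because all three uses in section 12.1.5 are statements about change, and the output is purely descriptive. Zeros created by the rule would enter the mean, the spread and the CSC percentage, and a reader could not tell them from observed zeros.

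The assumed value also fits poorly with the plan's own expectation. Baseline is normally taken during inpatient care (sections 8 and 10.8; some enrolment may follow discharge), and section 12.1.3 says that "clinical improvement may be expected with the passage of time (i.e., without eYST), especially post inpatient admission". Nor is the rule cautious in every direction. A lost youth cannot be counted as improved, but cannot be counted as worse either. Section 9.2 allows withdrawal of participants who cannot be reached or who are judged adversely affected. Such a youth, if no final assessment is obtained, would be recorded as unchanged.

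**Working it through.** **Inputs.** N = 20 youth (section 12.1.3). Visits for the listed measures: W0 and W12 (sections 1.3 and 10.8). No dropout rate is stated, so m, the number lost with no post-baseline value, is assumed to be 2, 3 or 5. The figure of 5 is the gap between 20 and the 15 users that section 12.1.3 cites for usability problems; it is an illustration, not a stated allowance. All 20 are assumed to have a baseline and to form the denominator, because section 12.1.5 names none. Write n = 20 − m.

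**The plan's own figure.** The planned 20 cannot be reproduced without a dropout rate. Inflating 15 gives exactly 20 at an assumed 25% loss: 15 / (1 − 0.25) = 20. Losses of 15%, 20% and 30% give 18, 19 and 22. This shows consistency only.

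**One lost youth.** Imputed W12 = W0, so change = W0 − W0 = 0 for any baseline score. An index that divides change by a standard error is also 0. The documents do not reproduce the CSC thresholds, but the conclusion needs only that CSC requires a non-zero change.

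**Mean change.** Mean with the rule / observed-case mean = n/20.
- m = 2: 18/20 = 0.90
- m = 3: 17/20 = 0.85
- m = 5: 15/20 = 0.75

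**CSC percentage.** If k of the observed youth meet CSC, the rule reports k/20. The possible values run from k/20 (none of those lost) to (k + m)/20 (all of them), so the reported figure is always the lower end. The width is m/20, which is 10, 15 or 25 points. Example with m = 5 and an assumed k = 8: observed cases 8/15 = 53.3%; rule 8/20 = 40%; range 40% to 13/20 = 65%. The same algebra applies to deterioration, so that percentage is also put at its lowest possible value.

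**Does this measure bias?** No. Suppose those lost truly changed by f times the mean of those observed. Then true mean / observed-case mean = (n + m·f)/20. For m = 5, where the rule always gives 0.75 and observed cases always 1.00:

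| f | true ratio |
|---|---|
| −0.5 | 12.5/20 = 0.625 |
| 0 | 15/20 = 0.75 |
| 0.5 | 17.5/20 = 0.875 |
| 1 | 20/20 = 1.00 |

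The rule's error is −m·f/20 and the observed-case error is m(1 − f)/20. They are equal in size at f = 0.5 (0.125 each for m = 5). Observed cases are nearer the truth only when f exceeds 0.5.

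**Which outcomes are outside this.** SUS, FIM, AIM, IAM and CSQ-I have no W0 value in Table 1, so no baseline can be carried. The Cornell Services Index is at W0 and W12 in Table 1, but the schema in section 1.2 also lists it at week 4/8. Until those are reconciled, the result cannot be applied to it.

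**The case against.** The best defence is that no decision rests on these outcomes. Section 12.1.3 rules out conclusive statements about effect, section 12.1.5 asks for great caution, and the success criteria in section 12.1.1 use SUS and uptake measures. Treating a lost youth as not improved is also a cautious choice in an uncontrolled study that expects spontaneous improvement. The lower CSC bound proposed below is the same number that the rule reports. Retention is encouraged by payments that rise to $35 at week 12 (section 8.7), and an early final assessment may be obtained (section 12.2). All of this stands and keeps the point minor. It does not remove the need to show which values were observed, and the caution does not extend to worsening, which the rule hides.

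Four stronger readings are tempting, and the documents do not support them.

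- A reader might infer that the rule is more biased than an observed-case analysis, or that it understates true improvement by 10% to 25%. Those percentages compare it with the youth who were observed. Which is nearer the truth depends on f, which is unknown.
- A reader might infer that carrying W0 C-SSRS forward would count the index episode as a follow-up event. The W0 look-back period is not stated and section 12.1.2 does not name C-SSRS. What can be said, with less confidence, is that follow-up asks about an attempt since baseline (Appendix B, definition of high risk) and a W0 interview cannot answer that.
- A reader might infer that the comparison with the former YST trial is distorted. That trial's handling of missing data is not given, so no discrepancy is shown.
- A reader might take 5 lost youth as the planned allowance. The 15 behind it is a number for detecting usability problems, not for week-12 clinical follow-up.

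**Conclusion.** The point holds as a minor weakness of the analysis plan. For the six measures scheduled only at weeks 0 and 12, the stated rule is baseline carried forward. A youth with no post-baseline value is given a change of exactly 0 and can be counted neither as meeting CSC nor as worse. That part follows directly from the schedule. The size rests on assumptions: 2, 3 or 5 of 20 lost, every youth with a baseline, and all 20 in the denominator. The optional final assessment reduces the number affected but does not cure the rule, since it may not be obtained. Neither the carried-forward figure nor the observed-case figure should stand alone.

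**What to change.** Amend section 12.1.2 for the measures scheduled only at weeks 0 and 12, so that the carried-forward result is not the only one shown.

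1. Report change and CSC for youth with an observed week-12 value, with n and the reasons for missing values, and state that they may not represent those lost.
2. List any earlier final assessment obtained under section 12.2 separately, with its week. Counting it as a week-12 value would be carrying forward under another name.
3. Give bounds for the CSC percentage: all missing without CSC, then all missing with CSC. Do the same for deterioration if it is tabulated.
4. If the carried-forward analysis is kept, label it 'baseline carried forward' and show it beside these results.
5. Do not carry W0 C-SSRS forward as a follow-up finding.
6. In the comparison with the former trial (section 12.1.5), state how missing data were handled on each side.
7. Reconcile the timing of the Cornell Services Index between sections 1.2 and 1.3 before any rule is applied to it.

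None of this needs a model, so it respects the plan's sample-size argument. The cost is a few lines of wording, with no extra data, visits or participants. The drawback is that n falls below 20 if any youth is lost, and some results appear as a range.
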